### **11. PROCEDURES INVOLVED\***

The ViTrack as outlined above will be utilized to obtain BP readings throughout the surgical procedure. This will allow us to compare BP readings between the non-invasive ViTrack device and the invasive intra-arterial catheters that are currently being used to obtain readings. The device will apply minimum force on wrist. This force will be similar to the forces applied by the fingers on the skin over the radial artery at the wrist while manually feeling the pulse.

## INVESTIGATOR STUDY PLAN - REQUIRED

Step by Step procedures:

- 1) A signed fact sheet and HIPAA authorization will be obtained prior to surgical visit.
- 2) Upon admission for surgical visit the patient will be prepped in the operating room.
- 3) A radial intra-arterial catheter will be placed on one wrist as standard of care.
- 4) The ViTrack BP measuring device will be placed on patient's other wrist.
- 5) Data will be simultaneously recorded from both the ViTrack and arterial catheter in opposite wrists.

Data collection from both the ViTrack and arterial catheter in opposite wrists will be zero-referenced to the external auditory meatus for supine patients. Both the invasive BP monitor and the ViTrack will produce an analogue output signal, the strength of which will relate to BP. When optimally calibrated the ViTrack's analog output signals should mirror that of the invasive arterial signals. To avoid discrepancies due to the internal software of the two devices, the analog signals will be sampled directly from both devices and the data will be processed through the same analog-to-digital converter and simultaneously recorded on the data-logging computer. Results and de-identified data will be securely shared with the sponsor utilizing data sharing methods below.

A member of the UMASS study team will be present to collect necessary study data; sponsor will not be present in the operating room. At the end of surgery, we will collect the device and inspect extremity on which ViTrack had been placed. We will assess environmental factors pertaining to the devices clinical use and utility as well as its comfortability, any irritations, if it caused any stress, and if the patient thinks the device could be worn for long periods of time.

Data to be collected: Age; gender; height; weight; wrist circumference of dominant arm; history of high BP, diabetes, high cholesterol and cardiovascular disease; and BP and heart rate (HR) measurements from the two devices. Once data is de-identified data will be shared with the sponsor.

### **12. DATA AND SPECIMEN BANKING\***

NA- There is no specimen collection for this study. No data will be specifically banked for use in future studies, however fully de-identified study data will be shared among study collaborators and may be used to perform later data analysis

### **13. Data Analysis and Management\***

A minimum of 255 data points will be selected by random computer generator from each patient's arterial line and ViTrack recordings. The analysis of 255 time points per patient will be used to compare ViTrack with arterial line measurements. For each sample data point, a "ten beat epoch average" will be calculated, i.e. four beats prior and six beats after (including the sample point itself) will be averaged. Differences in device readings will be calculated as ViTrack minus arterial line values. In addition, Bland Altman plots will be used to determine agreement between the two devices. Our protocol will greatly exceed the AAMI guidelines by examining 255 paired measurements per patient for a minimum total of 5100 time points across 30 patients.

## **INVESTIGATOR STUDY PLAN - REQUIRED**

A sample size estimate was determined using the Bland-Altman method within MedCalc. Assuming an alpha error of 0.05, a beta error of 0.1, expected mean of differences of 5 mm Hg, expected standard deviation of 10 mm Hg, and maximum allowed differences between methods of 26 mm Hg, we calculated the minimum number of pairs to be 1570 which should be obtained with the number of subjects we propose to study

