### **10. STUDY ENDPOINTS\***

- a. The primary and secondary outcome measures: accuracy of ViTrack in measuring BP continuously as determined by use of Bland-Altman plots
- b. Any primary or secondary safety endpoints: Observing for local skin irritation

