### **25. LOCAL NUMBER OF SUBJECTS**

Thirty (30) patients will be recruited between the University and Memorial Campuses. We are allowing a screening failure of 50% (significant differences in BP between arms; inability to insert arterial catheter).

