## Statistical and Data Analysis Plan:

A total of n=30 patients were recruited to optimize the ViTrack technology and compare its performance to radial invasive arterial lines. A total of n=24 patients were used to optimize hardware, device form factor, algorithms, and usability. Then, we used the updated version of the ViTrack device to compare the device performance on 6 patients undergoing vascular surgery in the University of Massachusetts Medical School.

The data was analyzed following the AAMI SP10:2008 standard. Both ViTrack and Invasive arterial pressure data were averaged over a 20-second non-overlapping window, thus providing a paired measurement for comparison every 20 seconds. The average length of the surgery was ~3 hours. After clearing out the segments (both in IAP and ViTrack) affected by motion artifacts, we used the remaining segments for accuracy analysis. Since each dataset might not have a similar number of data points to compare, we weighted the samples to avoid bias to one dataset. A total of 2800 data points across 6 subjects were used for comparison. As per the FDA standard ANSI/AAMI SP10:2008 or the newly adopted ISO 81060-3:2022 standard, the mean error should be <5mmHg or <6mmHg and the standard deviation should be <8mmHg or <10mmHg respectively. We have analyzed ViTrack data on 6 patients and showed the results in **Figure 1** below. ViTrack showed far higher accuracy for both SBP (mean error = 0.19 mmHg [SD = 5.70 mmHg]) and DBP (mean error = 0.90 mmHg [SD = 5.97 mmHg]) measurements when compared to either of the recognized standards [**Fig1**].

**Fig 1: Performance of ViTrack Vs. IAP after motion artifact correction in 6 operating room patients undergoing vascular surgery.**

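### The 90% power attached to 1,570 pairs treats repeated readings as independent, so it is unsupported unless within-patient correlation is very small; the SAP text gives no patient-level precision

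*Protocol*

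**What the plan says.** The sample-size paragraph in Protocol section 13 uses a Bland-Altman calculation in MedCalc with alpha 0.05, beta 0.1, expected mean difference 5 mmHg, expected SD 10 mmHg and maximum allowed difference 26 mmHg. It ends: "we calculated the minimum number of pairs to be 1570 which should be obtained with the number of subjects we propose to study".

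The pairs are repeated readings within patients. Section 13 states: "A minimum of 255 data points will be selected by random computer generator" per patient, "for a minimum total of 5100 time points across 30 patients". Section 25 states: "Thirty (30) patients will be recruited between the University and Memorial Campuses". The endpoint in section 10 is "accuracy of ViTrack in measuring BP continuously as determined by use of Bland-Altman plots".

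The SAP reports on a smaller set: "A total of 2800 data points across 6 subjects were used for comparison". Because counts differed between patients, "we weighted the samples to avoid bias to one dataset". Its text then gives mean error and SD: 0.19 (SD 5.70) mmHg for SBP and 0.90 (SD 5.97) mmHg for DBP.

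Neither text mentions an ICC, a design effect, a repeated-measures form of the limits of agreement, or a confidence interval for the bias, the SD or the limits.

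**The concern.** Readings from one patient share that patient's anatomy, sensor placement, calibration and any difference between the two arms. If the device reads a few mmHg high in one patient, it will tend to do so in most of that patient's pairs. Such pairs carry less information than the same number from different patients, and beyond a certain point only more patients add precision.

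A sample size stated as a count of pairs hides this. If only the count mattered, 7 patients would do, since 7 x 255 = 1,785 exceeds 1,570. The SAP's 2,800 points from 6 patients also exceed 1,570, so a reader relying on the protocol's figure could take that set as adequately sized. At stake are the only sample-size justification in the documents and the reader's ability to judge how precisely the reported accuracy is known.

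**Working it through.** **1. Reproduce the protocol's figure.** Inputs are from Protocol section 13. The expected upper limit of agreement is 5 + 1.96 x 10 = 24.6 mmHg, which leaves 26 - 24.6 = 1.4 mmHg. For n independent pairs, SE = SD x sqrt(1/n + 1.96²/(2(n-1))) and power = Phi(1.4/SE - 1.96). The smallest n with power of at least 0.90 is 1,567 (SE 0.432). At n = 1,570 power is 0.901. A one-sided version gives about 1,278, so the two-sided 95% interval of the limit, with independent pairs, is what lies behind the figure.

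**2. Count the planned pairs.** 30 x 255 = 7,650. The protocol's own total of 5,100 equals 20 x 255. Either is well above 1,570, so the count itself is met.

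**3. Allow for clustering.** Assumptions: a random-intercept model with exchangeable correlation, and total SD held at 10. With k patients and m pairs each:

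- sb² = 100 x ICC, sw² = 100 x (1 - ICC), a = sb² + sw²/m
- Var(S²) = 2a²/(k-1) + 2sw⁴(1-1/m)²/(k(m-1))
- SE² = a/k + 1.96² x Var(S²)/(4 x 100)

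Example for k = 30, m = 255, ICC 0.1: a = 10 + 90/255 = 10.353 and Var(S²) = 9.50. Then SE² = 0.345 + 0.091 = 0.436, SE = 0.661, and power = Phi(1.4/0.661 - 1.96) = 0.56.

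| ICC | SE | 95% half-width of limit (mmHg) | Power, 30 x 255 | Power, 30 patients, unlimited points |
|---|---|---|---|---|
| independent | 0.195 | 0.4 | >99% | – |
| 0.05 | 0.470 | 0.9 | 85% | 90.5% |
| 0.1 | 0.661 | 1.3 | 56% | 60% |
| 0.2 | 0.983 | 1.9 | 30% | 31% |
| 0.3 | 1.276 | 2.5 | 19% | 20% |

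Power stays at 90% up to ICC 0.041 for 30 x 255, and up to 0.025 for 20 x 255. With unlimited points, 30 patients hold 90% up to ICC 0.051. Simulation that re-estimates the variances and uses a z interval gives 83%, 57%, 34% and 25% at ICC 0.05, 0.1, 0.2 and 0.3. That rule is somewhat liberal at the higher values, so the formula figures are preferred.

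For the 7 patients mentioned above, the same formula gives about 71% power at ICC 0.01 and 17% at 0.1.

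**4. How far the loss depends on the inputs.** At ICC 0.3 with 30 x 255, simulated power against 26 mmHg is 50% for mean 4 and SD 10, but 99% for mean 0 and SD 10, or for mean 5 and SD 8. The loss comes from the 1.4 mmHg margin.

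**5. Precision of the SAP's mean errors.** Assumptions: k = 6, equal counts m = 2800/6 = 467, equal weights, and the reported SD taken as total SD. Half-width = 2.571 x sqrt(a/6), with t on 5 df.

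- SBP, ICC 0.1: a = 5.70² x (0.1 + 0.9/467) = 3.31, giving 1.9 mmHg. At ICC 0.3: a = 9.80, giving 3.3.
- DBP, ICC 0.1: a = 3.63, giving 2.0 mmHg. At ICC 0.3: a = 10.75, giving 3.4.
- Points treated as independent: 1.96 x 5.70/sqrt(2800) = 0.21 and 1.96 x 5.97/sqrt(2800) = 0.22.

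**The case against.** **The ICC is unknown, so the power statement has not been shown to be wrong.** This stands. A reader might infer that the stated power is incorrect or the study underpowered. The documents do not support that: below an ICC of about 0.04 the 90% holds. Nor does the protocol say that the pairs are independent; this is inferred because the independent-pairs formula returns its figure. The fair description is unsupported.

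**More points could be taken per patient.** This stands in part. The protocol sets 255 as a minimum, and between ICC 0.041 and 0.051 extra points do bring 30 patients back to 90%. It is tempting to say that extra points can never help, but that is true only above about 0.05.

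**No test against 26 mmHg is planned.** This stands. The endpoint is accuracy by Bland-Altman plots. If the SAP's means and SDs were the true values, even 6 patients would have at least 99% power against 26 at ICC 0.3. The SAP is also written in the past tense, so rewording the sample size changes no enrolment decision.

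**The SAP weights the samples.** Weighting stops a patient with many points from dominating the estimate. It does not say how precise the estimate is.

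**Figure 1 of the SAP may show limits or intervals.** It may; it is not visible here. The point is confined to the SAP's text.

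**The SAP's results meet its limits.** Its point estimates do, including the one that "the standard deviation should be <8mmHg or <10mmHg respectively". A reader might infer from wide intervals that the device misses the standard. The SAP states no criterion on a confidence bound, so that inference is not supported.

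**Conclusion.** The point holds as a fault of method and reporting that should be fixed. The figure of 1,570 carries beta 0.1 only for independent pairs. With 255 pairs from each of 30 patients, the 90% power needs an ICC no higher than about 0.04, or about 0.025 if the stated 5,100 pairs mean 20 patients. Above about 0.05, no number of points per patient restores it with 30 patients. The half-width of the upper limit grows from 0.4 mmHg to 1.3 at ICC 0.1 and 2.5 at ICC 0.3.

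The second part is that the SAP's text reports mean error and SD from 6 patients with no interval. The plausible half-width of the mean error is about 2 to 3.5 mmHg for ICC 0.1 to 0.3, some ten times or more what the 2,800 points suggest.

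These sizes rest on an assumed ICC range, exchangeable correlation, a total SD as stated, and, for the SAP, equal counts and weights. The actual power cannot be stated from the documents. The practical reach is modest, since the power loss belongs to one narrow margin that no planned test uses.

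**What to change.** In the sample-size paragraph of Protocol section 13, withdraw the statement that 1,570 pairs deliver beta 0.1. Restate power, or the expected half-width of the limits of agreement, by number of patients over a stated ICC range. For 30 x 255 at the present inputs this would read 85%, 56% and 19% at ICC 0.05, 0.1 and 0.3. Reconcile 5,100 with 30 x 255 = 7,650 at the same time.

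In the analysis text of section 13 and in the SAP, use Bland-Altman limits for repeated measurements, built from between- plus within-patient variance, and report both components. Give mean error, SD and limits with patient-level confidence intervals suited to few clusters (with 6 patients, for example, t on 5 df for the mean and a variance-component interval for the SD). State whether each is one- or two-sided. Present them as precision, without adding an acceptance rule on confidence bounds against 8 or 10 mmHg.

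The cost is rewording and some further analysis of data already held, with no added patients. The downside is a less favourable power statement and wider intervals.

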### **14. PROVISIONS TO MONITOR THE DATA TO ENSURE THE SAFETY OF SUBJECTS\***

The ViTrack device is non-invasive and involves minimal risk to the patient. However, we will monitor skin integrity at the device placement site for skin irritation. There are no plans to form a data safety monitoring plan nor to perform an interim statistical analysis.

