## INVESTIGATOR STUDY PLAN - REQUIRED

A minimum of 30 subjects will be recruited in groups of 5. An analysis of 255 time points per patient will be used to compare ViTrack with arterial line measurements. If the bias exceeds the standards, the algorithm will be further optimized. Subsequently, an additional 5 subjects will be recruited, and the same protocol will be applied so that the correction, if required, may be validated.

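### The protocol ties re-tuning to an accuracy check yet plans no interim analysis, and neither document defines the comparison set by an algorithm lock

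*Protocol*

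**What the plan says.** **Protocol, section 4 (Objectives, last paragraph).** "A minimum of 30 subjects will be recruited in groups of 5". On the accuracy check: "If the bias exceeds the standards, the algorithm will be further optimized". After that, "an additional 5 subjects will be recruited, and the same protocol will be applied so that the correction, if required, may be validated". The protocol gives no numeric limit for this trigger, no number of checks, and no point at which hardware and algorithm are frozen.

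**Protocol, section 14.** The section on safety monitoring intends neither a data safety monitoring plan "nor to perform an interim statistical analysis". The wording is not restricted to safety data.

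**Protocol, sections 13 and 25.** The comparison uses "255 paired measurements per patient for a minimum total of 5100 time points across 30 patients". Section 25 gives the same headcount: "Thirty (30) patients will be recruited between the University and Memorial Campuses". Neither section sets aside patients used for tuning or recorded with an earlier version.

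**SAP, Statistical and Data Analysis Plan.** "A total of n=24 patients were used to optimize hardware, device form factor, algorithms, and usability". The updated device was then compared with the arterial line in 6 vascular surgery patients, giving 2800 data points. Numeric limits appear only here: mean error below 5 or 6 mmHg and SD below 8 or 10 mmHg, depending on the standard. The SAP is written in the past tense and contains its results.

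**The concern.** A decision to re-tune cannot be made without analysing accuracy against a limit. If that happens while patients are still being enrolled, it is an interim analysis in the ordinary sense, and section 14 says none is planned. As a result, no rule covers how many checks there may be, what triggers a change, or when changes stop.

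The second problem is the analysis set. Followed as written, section 13 could combine readings from several algorithm versions and include patients on whom the algorithm was tuned. The result would describe no single device. The SAP does something different and better, since it keeps tuning and comparison patients apart. But the protocol does not foresee the split, and the SAP does not say how the boundary between patient 24 and patient 25 was set.

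The SAP's claim to beat recognized standards rests on these 6 patients. That claim has its usual meaning only if the device was frozen before their data were seen and every patient measured afterwards was counted.

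**Working it through.** **1. The plan's own figures.** Section 13 gives 1570 pairs (two-sided alpha 0.05, power 0.90, mean difference 5, SD 10, maximum allowed difference 26 mmHg). With SE = SD × √(1/n + 1.96²/(2(n−1))), the confidence limits of mean ± 1.96 SD must lie inside ±26. This gives n = 1568, so the figure reproduces. It is a calculation for one analysis of independent pairs, with no allowance for repeated checks or re-tuning.

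The total in section 13 does not match its own headcount: 255 × 30 = 7650, while 5100 / 255 = 20 patients. So the documents imply comparison sets of 30 (sections 13 and 25), 20 (from the 5100 total) and 6 (SAP).

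**2. The sections side by side.**
- Section 4 makes re-tuning depend on an accuracy result; section 14 plans no interim statistical analysis.
- Section 4 validates a correction on 5 additional subjects; the SAP compares on 6.
- Section 4 recruits in groups of 5; the SAP's boundary falls at 24, which is not a multiple of 5.
- Section 6 admits patients having any surgery or in intensive care; the SAP's 6 all had vascular surgery, and no reason is given.
- The SAP gives a sequence (optimize, then compare with the updated device) but no version lock, and no statement that the 6 were named beforehand or were all the patients measured after the update.

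**3. What repeated chances to pass could do (illustration).** Inputs: the 5 mmHg limit from the SAP; group size 5 from section 4; true bias 6 mmHg, between-patient SD of 3 to 5 mmHg and no gain from re-tuning, all assumed. A pass here means only that the group mean is within ±5 mmHg.

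The SE of a group mean is SD/√5, which is 1.342 for SD 3 and 2.236 for SD 5. The pass probability for one group is p ≈ Φ((5 − 6)/SE), that is Φ(−0.745) = 0.228 and Φ(−0.447) = 0.327. The lower limit of −5 adds nothing visible.

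| Chances to pass | Formula | SD 3 | SD 5 |
|---|---|---|---|
| One group of 5 | p | 0.23 | 0.33 |
| At least one of two | 1 − (1 − p)² | 0.40 | 0.55 |
| At least one of six | 1 − (1 − p)⁶ | 0.79 | 0.91 |

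The second row corresponds to one check, one re-tuning and one extra group. The third applies only if every group were checked and any single pass accepted. At true bias 7 mmHg, one group gives 0.07–0.19 and six give 0.35–0.71.

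**4. Adding the SD limit.** A simulation required |mean| ≤ 5 and SD ≤ 8 mmHg, with 255 independent readings per patient and a between-patient share of variance of 0.2 to 0.7 (assumed). For a device with true mean error 6 and SD 8 mmHg, the pass rates were:
- one group of 5: 19–26%
- at least one of six groups: 71–84%
- one fixed set of 6 fresh patients: 17–25%
- one fixed analysis of all 30: 4–12%

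The inflation comes from repeated chances to pass, not from having 30 patients in the set.

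**The case against.** **Section 4 may describe a single check.** It can be read as one analysis after the minimum of 30, followed by a fresh group of 5. On that reading there is no look within the first 30, and the conflict with section 14 largely goes. A reader might infer that accuracy is tested after every group of 5; that is plausible, but the text does not say it. What stands is that the text leaves both readings open.

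**Section 14 is about safety.** Engineering checks on bias could be held to lie outside it. But its wording covers any interim statistical analysis, and no other section describes the check.

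**The SAP does not count all 30.** A reader of section 13 alone might infer that tuning patients are inside the reported accuracy result. By the SAP's own account they are not. Using fresh subjects, as both documents do, is sound in principle.

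**Pooling need not favour a pass.** A reader might infer that mixing tuning and validation patients biases the result towards success. Section 13 does not say that earlier recordings would be reprocessed with the tuned algorithm. Left as recorded, data from earlier failing versions would tend to worsen the estimate. The objection to pooling is that it mixes versions and tuning data; no direction of bias is established.

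**A missing lock statement is a gap in documentation, not evidence of selection.** This is right. The numbers 24 and 6 show a departure from the protocol's grouping and nothing more.

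**Conclusion.** The point holds in limited form. Sections 4 and 14 must be reconciled, because the first requires an accuracy analysis that may fall during enrolment and the second plans none. Section 13 and the SAP disagree on which patients form the comparison. The SAP gives neither a lock nor a statement that the 6 were fixed in advance or were all the post-update patients. The documents do not show that selection occurred, but they do not let a reader exclude it.

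The probabilities describe a borderline failing device under assumed between-patient variation and no benefit from re-tuning. On the narrow reading (one check, one extra group), the chance of at least one pass is 0.40–0.55 against 0.23–0.33 for a single group. A reader might take 0.79–0.91 as the plan's false-pass rate. The documents do not support that: it needs six checks, acceptance of any passing group and no SD limit. A true bias of 6 mmHg also sits at the boundary of the alternative limit the SAP cites.

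Nor do these figures show that the reported result was a chance pass. The SAP's mean errors of 0.19 and 0.90 mmHg, with SDs of 5.70 and 5.97 mmHg, are well inside the limits.

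**What to change.** **Protocol, sections 4 and 14.** State that accuracy checks made before the lock are interim analyses used only for tuning. Give their number or timing and the numeric trigger.

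**Protocol, section 13.** Replace the 30-patient comparison with all patients measured after hardware and algorithm are locked, their number fixed before the first of them is measured. Correct the 5100 total to agree with the set chosen.

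**SAP.** Give the lock point, the number of checks made before it, and confirmation that the 6 were all the patients measured after it. If that cannot be confirmed, label the result a development-stage estimate. For data already reported, these SAP statements carry the weight, because protocol wording can only govern patients still to be enrolled.

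**Cost.** The change is wording only and needs no new patients. The accuracy claim then rests on fewer patients than the protocol's 30. A lock removes repeated chances to pass but not the imprecision of a small set: in the simulation above, one fixed set of 6 still passes the failing device 17–25% of the time.
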